10.4 Stopping Rule

The study will be monitored to ensure that the occurrence of a specified set of treatment related serious adverse events (TRSAEs) during the 18 weeks of intervention does not substantially exceed an anticipated rate. The following TRSAEs will be considered for early stopping of either one of groups A or B:

- Death considered to be probably or definitely related to the inhaled CsA or
- Any grade IV toxicity considered to be probably or definitely related to inhaled CsA, i.e. opportunistic infection such as tissue-invasive CMV or *Pneumocystis carinii*, with exception of temporary cytopenias.

We will monitor the numbers of subjects who have developed any of the above specified TRSAEs using the stopping rule outlined below. The trial will be seriously considered for early stopping if the number of subjects in the trial who develop TRSAEs is over the pre-specified threshold value in the Table.

From experience using this agent in other clinical settings as detailed in the investigator's brochure, we anticipate the rate of developing at least one of the above specified TRSAEs to be 10% or less. Following Geller et al., our stopping rule is determined by a Bayesian approach²³. The stopping boundary for the trial is reached if the Bayesian posterior probability that the true probability of developing one or more of the above specified TRSAEs exceeds this benchmark rate of 10% is at

least 90%. We take our prior distribution to be a beta distribution with the sum of the two beta parameters to be 3, i.e. the parameters of the beta prior distribution are 0.30 and 2.70. Since we have seen in the past that the first few subjects to be accrued are possibly sicker than the rest of the subjects in the sample, we will start safety monitoring when 3 subjects have developed specified SAEs. The following table summarizes the threshold numbers for stopping either group A or B:

| Number of Subjects | Stop if the number of subjects who develop any of the number of specified TRSAEs reaches: |
|--------------------|---|
| ≤11 | 3 |
| $12 \le n \le 18$ | 4 |
| $19 \le n \le 25$ | 5 |
| $26 \le n \le 32$ | 6 |
| $33 \le n \le 39$ | 7 |

We investigated the performance of the above stopping rules by a simulation study. For the stopping rule, we generated a study with 39 independent Bernoulli trials, each had a probability p=.1 for having the above TRSAE and q=1-p for not having such TRSAE and compared the TRSAE outcomes with the above stopping boundary to determine whether the study was stopped. We repeated the simulation 100,000 times and computed the proportion of stopped studies (i.e. "number of stopped studies"/100,000), which were stopped using the above stopping rule.

The following table summarizes the proportions of stopped studies under a number of scenarios.

| Prob of specified TRSAE | 5% | 10% | 15% | 20% | 30% |
|---|------|-------|-------|-------|-------|
| Proportion of Stopped Studies | 2.2% | 20.2% | 51.5% | 77.4% | 98.1% |
| Average Number of Subjects | 38.4 | 34.5 | 27.8 | 21.0 | 11.9 |
| Average Number of Subjects Suffering TRSAE | 1.93 | 3.47 | 4.18 | 4.18 | 3.54 |

The DSMB will evaluate all serious adverse events and have all the required information to implement the above-defined monitoring plan. In addition, the DSBM may recommend early study termination if other unforeseen adverse events necessitate this decision.

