Treatment related SAEs (TRSAEs) are those attributed as possibly, probably or definitely. As

detailed in section 9.7 stopping rules, death and any grade IV toxicity considered to be possibly, probably or definitely related to CIS will be monitored and considered for early stopping the study according to statistically determined criteria.

Hospitalization (overnight admission) for routine supportive care (platelet or RBC transfusions) or admission from the NIH inpatient unit to the NIH ICU for routine monitoring will not be reported as a serious adverse event.

APT Pharmaceuticals, Inc.: A listing of all SAEs will be submitted to APT pharmaceutical quarterly. Safety reports will be reported as detailed in section 12.5.

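### The safety stopping rule is stated inconsistently: sections 10.4 and 12.2 count different events, and within 10.4 the prose trigger needs one more event than the table

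*Combined protocol and SAP*

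**What the plan says.** **Events counted.** Section 10.4 lists two kinds of event for early stopping of either group. The first is "Death considered to be probably or definitely related to the inhaled CsA or" and the second is grade IV toxicity at the same two attribution levels, "with exception of temporary cytopenias". The benchmark is set for that list: "we anticipate the rate of developing at least one of the above specified TRSAEs to be 10% or less". Section 12.2, Assessment of Adverse Event Severity and Relationship to Treatment, describes the same rule differently: "detailed in section 9.7 stopping rules, death and any grade IV toxicity considered to be possibly, probably or definitely related to CIS will be monitored". It does not repeat the cytopenia exception. Section 9 ends at 9.5, so there is no section 9.7. Section 12 also has two headings numbered 12.2; this is the second.

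**Trigger.** The prose of 10.4 says early stopping is seriously considered if the number of subjects who "develop TRSAEs is over the pre-specified threshold value in the Table". The table header reads: "Stop if the number of subjects who develop any of the number of specified TRSAEs reaches". Section 10.4 also gives the underlying criterion ("The stopping boundary for the trial is reached if the Bayesian posterior probability" that the true rate exceeds 10% is at least 90%) and reports a simulation of 39 subjects that "compared the TRSAE outcomes with the above stopping boundary to determine whether the study was stopped".

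**The concern.** A stopping boundary is useful only if everyone who applies it counts the same events and acts at the same count. Here both are open.

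The attribution conflict is the more substantive, because nothing in the documents settles it. Section 12.2 defines possibly related as its own category, so the two sets differ in fact. The benchmark, boundary and simulation were all built for the narrower set. Possibly related deaths or grade IV events, where they occur, would raise the chance of stopping above the published figures.

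The trigger conflict can be settled from the plan's own figures, but a reader who follows the prose needs one more event than the table at every n. Because the threshold rises with n, that can delay a stop by more than one event or lose it altogether. The published operating characteristics would then not apply.

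**Working it through.** **Inputs, all from section 10.4.** Prior Beta(0.30, 2.70); benchmark 10%; posterior cut-off at least 90%; monitoring starts at 3 events; maximum 39 subjects; thresholds 3, 4, 5, 6, 7 for n ≤ 11, 12–18, 19–25, 26–32, 33–39; simulated stopping proportions and averages at true rates of 5, 10, 15, 20 and 30%.

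**Step 1: reproduce the table.** After k events in n subjects the posterior is Beta(0.30 + k, 2.70 + n − k). The boundary is the smallest k ≥ 3 with P(p > 0.10) ≥ 0.90. This gives 3 (n = 3–11), 4 (12–18), 5 (19–25), 6 (26–32) and 7 (33–39), which is the table at every n from 3 to 39, read as *reaches*. At the last n of each band:

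| n | Threshold k | Posterior at k − 1 | at k | at k + 1 |
|---|---|---|---|---|
| 11 | 3 | 71.3% | 90.8% | 97.9% |
| 18 | 4 | 74.6% | 90.3% | 97.1% |
| 25 | 5 | 77.4% | 90.4% | 96.6% |
| 32 | 6 | 79.7% | 90.8% | 96.4% |
| 39 | 7 | 81.7% | 91.3% | 96.4% |

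At the first n of bands 2 to 5 (12, 19, 26, 33), one event fewer gives 88.9, 88.7, 89.1 and 89.7%, just short of 90%. Requiring k + 1 events (*is over*) amounts to waiting for a posterior of about 96% or more, not 90%.

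**Step 2: operating characteristics.** Exact recursion over 39 Bernoulli subjects, checked after each subject. Stop when count ≥ k (*reaches*) or count ≥ k + 1 (*is over*).

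| True rate | 5% | 10% | 15% | 20% | 30% |
|---|---|---|---|---|---|
| Stopped, published | 2.2% | 20.2% | 51.5% | 77.4% | 98.1% |
| Stopped, *reaches* | 2.5% | 19.5% | 50.5% | 77.9% | 98.2% |
| Stopped, *is over* | 0.4% | 7.2% | 29.8% | 60.4% | 94.9% |
| Mean subjects, published | 38.4 | 34.5 | 27.8 | 21.0 | 11.9 |
| Mean subjects, *reaches* | 38.4 | 34.7 | 28.0 | 21.0 | 11.8 |
| Mean subjects, *is over* | 38.9 | 37.7 | 33.9 | 27.9 | 16.9 |
| Mean with TRSAE, published | 1.93 | 3.47 | 4.18 | 4.18 | 3.54 |
| Mean with TRSAE, *reaches* | 1.92 | 3.47 | 4.20 | 4.19 | 3.53 |
| Mean with TRSAE, *is over* | 1.95 | 3.77 | 5.08 | 5.58 | 5.06 |

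The published stopping proportions lie within 1.0 point of *reaches* and 1.8 to 21.7 points from *is over*. The match to *reaches* is close but not exact. With 100,000 runs the Monte Carlo standard errors are 0.05, 0.13, 0.16, 0.13 and 0.04 points, and four of the five published values differ from the exact ones by about 4 to 6 of these. That does not change which reading the simulation used.

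**Step 3: what *is over* does to a trial that should have stopped.** Among trials that stop under *reaches*:

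| True rate | Stops one event later | Two to five events later | Never stops within 39 |
|---|---|---|---|
| 10% | 17.7% | 19.0% | 63.3% |
| 20% | 36.7% | 40.9% | 22.4% |

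**Step 4: event set (assumed rates).** The documents give no rate for possibly related events. Starting from 10% for the narrower set, a counted rate of 11, 12, 15 or 20% makes the current table stop 25.1, 31.2, 50.5 or 77.9% of trials instead of 19.5%. Combining both ambiguities, with the wider-set rate assumed to be 12% (or 15%):

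| | *is over* | *reaches* |
|---|---|---|
| Probably/definitely only, 10% | 7.2% | 19.5% |
| Possibly added, 12% (15%) | 14.3% (29.8%) | 31.2% (50.5%) |

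**The case against.** The strongest reply is that the documents largely resolve both points. On the trigger, the table header, the posterior criterion and the simulation all agree, and only one prose phrase departs from them. This is right: the trigger needs a one-phrase correction, and the *is over* figures show the cost of following that phrase, not a flaw in the boundary itself.

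On attribution, section 12.2 defers to the stopping-rule section, and everything numerical belongs to the 10.4 list. That deference reasonably explains the missing cytopenia exception, and the general definition of treatment-related SAEs in 12.2 can stand if 10.4 is a subset of it. It does not explain an explicit extra attribution level in a sentence about the stopping rule itself, and the section it points to does not exist.

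The step 4 scenarios all start at exactly 10%, whereas the plan expects 10% or less. At a counted rate of 5% the table stops only 2.5% of trials, so the effect could be much smaller.

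Other safeguards also limit the harm. The DSMB evaluates all serious adverse events and may recommend termination for safety (10.4, 11.1). Section 10.5.2 takes individual subjects with related grade IV toxicity off study drug. Group B is closed to enrolment. The prose calls for serious consideration of stopping, although the table header says to stop. These points bear on severity; they do not remove the ambiguity in the formal count.

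**Conclusion.** The concern holds, and the rule is wrong as written. The table is sound and follows from the stated prior, cut-off and three-event start. The prose trigger is the sentence out of line. Followed literally, it lowers the stopping probability by 12.3 points at a true rate of 10% (19.5 − 7.2) and by 17.5 points at 20% (77.9 − 60.4), and raises the mean number of subjects with an event at 20% from 4.19 to 5.58. These figures assume independent subjects and a check after each one.

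The attribution conflict between 10.4 and 12.2 cannot be resolved from the documents. Its size rests entirely on the assumed rates in step 4. The consequence is an ambiguous formal count, not a loss of safety oversight, so this should be fixed but does not undermine the design.

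**What to change.** - Reconcile 10.4 and the stopping-rule sentence of 12.2 to one event set, stating the attribution levels and whether temporary cytopenias are excepted. Which set to use is for the investigators and the DSMB; this review does not choose.
- If the wider set is adopted, justify the 10% benchmark afresh for it. If the benchmark changes, re-derive the boundary and re-run the simulation table.
- In the 10.4 prose, replace *is over* with *reaches*, to agree with the table, the posterior criterion and the simulation.
- In 12.2, correct the reference from section 9.7 to section 10.4, and renumber the duplicate 12.2 heading. The general definition of treatment-related SAEs can stay if 10.4 is meant as a subset.

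The cost is a few wording changes, with recalculation only if the benchmark moves. Adopting the wider set could mean more DSMB reviews.

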10.5 Off Study Criteria

10.5.1 Subject choice: Subjects may withdraw from the study at their request any time. The risks of withdrawing will be discussed, as will alternative treatment options. Those subjects who choose to withdraw will be strongly encouraged to participate in study assessments until he/she initiates alternative BO therapy. In this scenario, patients will be deemed off study-drug, but have the option to continue on-study.

10.5.2 Principal investigator decision:

Subjects will be taken off study drug during the 18 week period of intervention if they:

- Have disease progression (beginning at week 9) as defined by a 20% or more decline in FEV₁ on two successive measurements at least 2 weeks apart
- Have evidence of an NCI grade IV toxicity related to study drug administration

- Require >25% increase in one or more existing immunosuppressive agents or the addition of new systemic immunosuppressive therapies due to worsening symptoms related to BOS (sustained for 3 weeks, excluding adjustments made for target drug levels) after week 9 (see section 6.2.3).
- Develop worsening performance status, defined by ECOG score ≥ 3 (please see hematology supportive care guidelines)
- Develop disease relapse or a significant non-pulmonary transplant complication in which death is likely to occur prior to the conclusion of the 18 week study period
- Are unable to comply with the study visits or become severely ill and cannot comply with the intervention.
- Are unable to tolerate the 150mg dose of the inhaled CsA
- Develop severe pulmonary infection that fails to respond to conventional treatment or where no effective drug treatment exists
- Subject becomes pregnant

Subjects that have stopped study drug administration will be asked to complete the study assessments, as off-study drug participants, whenever feasible. Lung deposition studies and pharmacokinetic tests will not be performed in off-study drug participants. Chest CT and bronchoscopy will only be performed if clinically indicated. If off-study drug subjects are unable or unwilling to complete the study assessments, they will be referred back to their primary transplant team and will end study participation.

10.5.3 Completion of the study

Upon completion of the week 19 assessment, subjects will have completed study participation and be taken off study and referred back to their primary transplant team to continue post transplant monitoring and care. After Week 19 assessment is completed, subjects with stabilized or improved disease will be offered the option of continuing CsA on **an extended access protocol**.

11.0 DATA AND SAFETY MONITORING

11.1 Safety Monitoring

NHLBI DSMB: The NHLBI Data Safety and Monitoring Board will review the protocol at an interval to be determined by the DSMB. A progress report will be forwarded to the DSMB at these times and their recommendations will be expeditiously implemented. The DSMB may recommend early termination of the study for considerations of safety and efficacy.

Safety Monitoring:

Principal Investigator: Accrual, efficacy and safety data will be monitored by the Principal Investigator, [name] and [name]., Medically Responsible Investigator.

NIH IRB. Prior to implementation of this study, the protocol and the proposed consent and assent forms will be reviewed and approved by the properly constituted Institutional Review Board (IRB) operating according to Title 45 CFR 46. This committee will also approve all amendments to the protocol or informed consent, and conduct continuing annual review so long as the protocol is open to accrual or follow up of subjects.

FDA: An annual progress report, any amendments to the protocol, and any change in the status of the protocol will be forwarded to FDA to:

[name], MS, Regulatory Officer [name], Division Director Division of Special Pathogen and Transplant Products Central Document Room Center of Drug Evaluation and Research, FDA [name] (w) [contact]

APT Pharmaceuticals, Inc.: A copy of the annual progress report to FDA, any amendments to the protocol, and any change in the status of the protocol will be forwarded to

[name] [[contact]] APT Pharmaceuticals, Inc [name] Telephone Number Fax Number

NIH Radiation Safety Committee (RSC): NIH Radiation Safety Committee (RSC): Because the technetium 99m silver colloid deposition studies are research procedures and because the frequency of CT imaging exceeds that which is standard in this subject population, some of the radiation exposure is therefore determined as indicated for research purposes. The Radiation Safety Form 88-23a, which includes dosimetry calculations for the high resolution CT scans and lung deposition studies utilizing radio-labeled drugs, was submitted to the Radiation Safety Committee for review (c/o [name]., Clinical Protocol Administrator, NIH Radiation Safety Committee [contact]) for initial and triennial RSC review so long as the protocol remains open for subject accrual and intervention.

| | SCREEN | On stu medica | | | |
|---------------------------------------|-----------|------------------|--------|------------|--|
| PROTOCOL TIMEPOINT | Pre-study | Day 7 | Day 63 | Day 126 | |
| High resolution chest CT | | | | | |
| Radiolabeled Lung disposition studies | | | | | |

Data Management: The PI will be responsible for overseeing entry of data into an in-house password protected electronic system and ensuring data accuracy, consistency and timeliness. The principal investigator, associate investigators, research nurses and/or a contracted data manager will assist with the data management efforts. Data will be abstracted from Clinical Center progress notes as well as from progress notes forwarded from home physicians. Laboratory data from NIH will be imported electronically from CRIS into an in-house clinical trial database. Laboratory values from referring home physicians will be entered into the system.

In order to maintain subject confidentiality, all case report forms, study reports and communications relating to the study will identify subjects by an assigned unique identifier. Case report forms may serve as source data if needed. All human subjects personally identifiable information (PII) as defined in accordance to the Health Insurance Portability and Accountability, eligibility and consent verification will be recorded. Primary data obtained during the conduct of the protocol will be kept in secure network drives or in approved alternative sites that comply with NIH security standards. Primary and final analyzed data will have identifiers so that research data can be attributed to an individual human subject participant, e.g., a unique code, or minimum PII required for subject identification. All primary and analyzed data will be located on the secure P drive.

In accordance with local and federal regulations, the Investigator will allow APT Pharmaceuticals, Inc. personnel or their designee, access to all pertinent medical records in order to verify the data gathered on the case report forms and to audit the data collection process. The US Food and Drug Administration (FDA) may also request access to all study records, including source documentation for inspection.

End of Study Procedures: Data will be stored in locked cabinets and in a password protected database until it is no longer of scientific value. Federal law requires that an Investigator maintain all study records for the indication under investigation for two years following the date a Product Licensing Application is approved or, if no application is to be filed or if the application is not approved for such indication, until two years after the investigation is discontinued and the FDA is notified. The results will be posted to clinicaltrials.gov.

Loss or Destruction of Data: Should we become aware that a major breech in our plan to protect subject confidentiality and trial data has occurred, the IRB will be notified.

Source Documentation: Clinical data entered onto the Case Report Form (CRF) may serve as source documentation.

Clinical Trial Monitoring Plan: Monitoring Responsible Party/ Monitor: An experienced independent protocol monitoring group has been contracted by the NHLBI. They will objectively audit records for compliance with the protocol.

Monitoring will assure the adequate protection of human subjects, safety of subjects involved in clinical investigations and the integrity and quality of data. The monitor/ responsible party for monitoring will be trained to perform monitoring activities.

Monitoring may occur prior to the IRB approval of the study (protocol/ site initiation), routine monitoring (during the protocol life cycle), and study termination. The monitoring activities will verify regulatory compliance, NIH & DIR policy compliance, IRB regulatory compliance, subject record review, and protocol compliance. The monitoring activities will be documented and the reports will be made available to regulatory personnel.

12. NIH INTRAMURAL IRB AND NHLBI CD REPORTING

12.1 Expedited Reporting

Events requiring expedited reporting will be submitted to the IRB per Policy 801 "Reporting Research Events".

12.2 Reports to the IRB at the time of Continuing Review:

The PI or designee will refer to HRPP Policy 801 "Reporting Research Events" to determine IRB reporting requirements and timelines.

12.3 Reports to the CD:

The PI or designee will refer to NHLBI DIR guidelines to determine CD reporting requirements and timelines.

Treatment related SAEs (TRSAEs) are those attributed as possibly, probably or definitely. As

detailed in section 9.7 stopping rules, death and any grade IV toxicity considered to be possibly, probably or definitely related to CIS will be monitored and considered for early stopping the study according to statistically determined criteria.

Hospitalization (overnight admission) for routine supportive care (platelet or RBC transfusions) or admission from the NIH inpatient unit to the NIH ICU for routine monitoring will not be reported as a serious adverse event.

APT Pharmaceuticals, Inc.: A listing of all SAEs will be submitted to APT pharmaceutical quarterly. Safety reports will be reported as detailed in section 12.5.

12.4 IND Safety Reporting to the FDA (IND 109,707)

Because this study will be conducted under an IND, U.S. Government regulations 21CFR, Part 312.32 require the issuance of an IND Safety Report to the Food and Drug Administration (FDA) for all "serious" adverse events that are "unexpected" and for which there is a "reasonable possibility that the experience may have been caused by the drug." Such serious events that are characterized as fatal or life-threatening must be reported to the FDA within 7 calendar days of the sponsor's initial receipt of the information, whereas non-fatal and non-life threatening events must be reported within 7 calendar days.

No expedited IND Safety Report is required if the event is considered to be expected based either on the study drug product label, the underlying disease states, or the study procedures.

The Safety report will contain a full written summary detailing relevant aspects of the serious adverse events in question. In each written IND safety report, all safety reports previously filed with the IND concerning a similar adverse experience will be included and the significance of the adverse experience in light of the previous, similar reports will be discussed.

Where applicable, information from relevant hospital case records and autopsy reports will be included. The investigator will always provide an assessment of causality at the time of the initial report as described in 'Assessment of Causality'.

Follow up information regarding the subject's subsequent course will be submitted until the SAE has resolved, the subject's condition stabilizes (in the case of persistent impairment) or the subject dies.

